4.4.4 Procedures

Three county nutrition educators were recruited to participate. Before starting recruitment, the PI, program director and county nutrition educators met to review the program purpose, timeline and how to integrate intervention activities. Each nutrition educator works in one county. After meeting with the PI and reviewing the program, nutrition educators began recruiting churches in their counties via word of mouth, online searches, and face-to-face visits. Faith communities were recruited from May-November of 2018. A search of African-American faith communities and faith community-affiliated organizations was conducted via online searches, neighborhood canvassing, and word of mouth. Faith communities and faith community-affiliated organizations were contacted

via email, their Facebook sites, phone, community organization board meetings, or face-to-face visits.

Initial contact of churches was made by the PI or county nutrition educators. A total of 62 churches were approached. Contact was made with 36 to introduce the program and provide contact information to schedule a follow-up meeting if interested. Of the seven churches that expressed interest, three were ready to begin immediately and selected to start the program. No additional churches were selected because it was anticipated that the first three would be able to recruit the desired sample size of 40 participants. After agreeing to participate, lay leaders, educators, the faith community pastor and the PI helped to recruit church members through church announcements describing the program and flyers.

4.5 Measures

4.5.1 Participant Characteristics

At baseline, participants completed a survey assessing age, level of education and sex.

4.5.2 Program Feasibility (Aim 1)

Feasibility was assessed in three domains: 1) church and participant recruitment and retention - based on number of churches contacted that agreed to participate, and participant attendance at each class during the 18-week program; 2) nutrition educators' perceptions of feasibility – based on post intervention semi-structured interviews, and 3) participants' perceptions of feasibility – based on how many times per week they communicated with their partner, post intervention semi-structured interviews, and a nine item feasibility survey. The nine items were adapted from a 21 item feasibility survey

from a dyadic diabetes management program (Heisler & Piette, 2005). Survey items specific to diabetes management such as blood testing or medications were omitted. Questions for this dyadic study included: ‘My peer support partner helped me do things to improve my eating habits’, ‘I would work with my peer support partner again’, and ‘I helped my partner achieve their goals’. The survey consists of 5-point Likert items from 1=strongly disagree to 5=strongly agree. Cronbach’s alpha of 0.87 showed good internal consistency of the feasibility scale in this study.

Post-intervention semi-structured interviews were completed with a random sample of seven dyads from each church and the nutrition educator assigned to each church. Participants who completed the interview received a \$25 gift card. Participant feasibility questions included in the interview were: ‘What was your overall experience like working with a partner?’, ‘What made it easier or harder to work with a partner to achieve your health goals?’. Nutrition educator questions included in the interview were, ‘What were some of the barriers and facilitators of using dyads?’, ‘What aspects of this intervention would you keep, or change and why?’.

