4.6.4 Dyadic Cooperation (Aim 3)

Directed content analysis (Hsieh & Shannon, 2005) was used to analyze semi structured interviews. Deductive a priori coding guided by the TGDM was used to analyze dyad cooperation. Inductive coding was used to analyze participant's perceptions of program feasibility, and the influence of social and environmental factors that influenced their health. Transcripts were read and re-read to identify and

assign codes. Codes were grouped according to themes. Ten percent of transcripts were read by a second reviewer to compare codes, resolve discrepancies in coding, and interpret results.

Table 7. *Assessment Variables and Timeline*

Aim	Variable	Week Assessed	Analysis Method
Participant Characteristics	Participant characteristics	1(Baseline)	Descriptive statistics
Participant Characteristics	Baseline differences between church sites	1	ANOVA, Fisher's exact
Participant Characteristics	Baseline differences between those who did and did not complete the program	1	T-test
Feasibility	Church and participant recruitment and retention	1-18	Descriptive statistics
Feasibility	Feasibility Survey Scores, Dyad communication frequency	18	Descriptive statistics
Goal Attainment/Health Outcomes	Changes in FVI and PA and interactions	1, 9, 18	Mixed Model
Goal Attainment/Health Outcomes	Changes in SBP, BMI, weight and interactions	1, 9, 14, 18	Mixed Model
Feasibility; Goal Attainment; Dyad Interactions	Perceptions of feasibility, dyad interactions - challenges and strategies	18	Directed Content Analysis

- American Heart Association. (2014). Body mass index in adults. Retrieved from <https://www.heart.org/en/healthy-living/healthy-eating/losing-weight/bmi-in-adults>
- American Heart Association. (2017a). The facts about high blood pressure. Retrieved from <https://www.heart.org/en/health-topics/high-blood-pressure/the-facts-about-high-blood-pressure>
- American Heart Association. (2017b). Suggested servings from each food group. Retrieved from <https://www.heart.org/en/healthy-living/healthy-eating/eat-smart/nutrition-basics/suggested-servings-from-each-food-group>

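### Does stopping church selection at three leave the church-recruitment measure in Aim 1 undefined and understated?

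*Combined protocol and SAP*

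**What the plan says.** Section 4.5.2 (Aim 1) lists church and participant recruitment and retention as the first of three feasibility domains. The church part is "based on number of churches contacted that agreed to participate". The section does not define agreement and gives no number for the denominator.

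The counts are in section 4.4.4. "A total of 62 churches were approached". Then: "Contact was made with 36 to introduce the program and provide contact information to schedule a follow-up meeting if interested". Then: "Of the seven churches that expressed interest, three were ready to begin immediately and selected to start the program". The reason for going no further is also given: "No additional churches were selected because it was anticipated that the first three would be able to recruit the desired sample size", that size being 40 participants. The next sentence moves on to recruiting members once agreement was in place, and says nothing of the four interested churches that were not selected.

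Table 7 (section 4.6.4) has a row for "Church and participant recruitment and retention", covering weeks 1 to 18, with descriptive statistics as the method. Section 4.4.3 says that statistical significance is not an aim of the study.

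**The concern.** Two features look troublesome when 4.5.2 is read against 4.4.4.

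The first is the numerator. The measure counts churches that agreed, but 4.4.4 gives no count under that name. The nearest figure is the three selected, and the investigators' own decision helped to fix that number. If some of the other four were willing and were left out only because the study had enough, three measures study capacity as well as church willingness, and it would be a lower bound.

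The second is the denominator. Section 4.4.4 uses the language of contact in two ways. It says of the whole outreach effort that "Faith communities and faith community-affiliated organizations were contacted" by several routes, and it also says contact was made with 36 of the 62. A reader could divide by either.

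At stake is the planning value of the result. This is the only church-level recruitment measure in Aim 1. Someone designing a larger study might take three of 36 as the share of churches willing to join and plan far more outreach than is needed.

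**Working it through.** The plan prints no church uptake rate, so there is no figure to reproduce. The check is to see how far the answer can move under each reading, and then whether anything in the plan depends on it.

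**Inputs (all from section 4.4.4).** Approached: 62. Contact made: 36. Interested: 7. Selected: 3.

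**Steps of the funnel.**
- Approached to reached: 36/62 = 58.1%
- Reached to interested: 7/36 = 19.4%
- Interested to selected: 3/7 = 42.9%

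**Uptake under each reading.** Let k be the number of the four unselected churches that agreed (k is not stated; range 0 to 4, assuming no church agreed without first showing interest). Uptake = (3 + k)/n.

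| k | n = 36 | n = 62 |
|---|---|---|
| 0 | 3/36 = 8.3% | 3/62 = 4.8% |
| 2 | 5/36 = 13.9% | 5/62 = 8.1% |
| 4 | 7/36 = 19.4% | 7/62 = 11.3% |

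With the denominator held fixed, the largest possible understatement is 7/3 = 2.3-fold, and the smallest is none. Each church moves the figure by 1/36 = 2.8 percentage points. Changing numerator and denominator together gives (7/36)/(3/62) = 4.0-fold.

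**Which reading does the text favour?** For the denominator, 4.5.2 names churches contacted, and 4.4.4 separates those approached (62) from those with which contact was made (36). The natural match is 36. The looser use of the word earlier in 4.4.4 leaves only mild doubt. For the numerator, the one reference to agreement in 4.4.4 comes directly after the selection of the three, which points to three without defining it. Two reasons are given for three: those churches could start at once, and they were expected to be enough. Only the second is a cap set by the study. The first is a property of the churches, and the other four are not described as having it.

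**What depends on the figure?** There is no feasibility threshold, no hypothesis test and no sample size that takes church uptake as an input. The sample size in 4.4.3 rests on interview saturation and 30% attrition. Enrolment there was 18 + 24 + 38 = 80 against a target of 40, so stopping at three churches did not leave the study short.

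**The case for a change.** The strongest argument for a change is that a reader can compute the bounds but not the measure itself. Only the investigators know what became of the four churches, and the fix would cost two sentences and a look at the recruitment notes. In a study whose purpose is feasibility in churches, uptake is a figure that others will carry forward, and 8.3% and 19.4% imply different outreach: about 10 × 36/3 = 120 contacts for ten agreeing churches against 10 × 36/7 = 51.

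Part of this stands. The status of the four is not stated, and giving it would be good reporting. It does not make the plan wrong. The document describes recruitment already completed, and the text available contains no results, so the outcome of the four churches is a matter for the report. Defining agreement as agreement whether or not selected would settle who is counted, but not what counts as agreeing. The outreach projection turns on three to seven churches found by word of mouth, online search and visits in three counties. These are not a random sample, and confidence intervals around such counts would suggest a precision they do not have. Even taken at face value, exact 95% intervals overlap widely: 1.8% to 22.5% for 3/36 and 8.2% to 36.0% for 7/36.

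**Conclusion.** The wording gap is real, but it is one that an analyst fills sensibly from the counts already printed. Depending on the unknown status of four churches, agreement lies between three and seven of the 36 reached, 8.3% to 19.4%. This assumes that agreement requires prior interest and that the denominator is the 36 churches with which contact was made. Bias is possible and not demonstrated: three may be exact. Because the full funnel and the reason for stopping are disclosed, no uptake rate is claimed, and the measure is descriptive with nothing hanging on it, following the plan as written gives no wrong result and no altered conclusion. No change to the plan is called for.

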4.5.3 Goal Attainment and Health Outcomes (Aim 2)

Weight, blood pressure, and BMI were measured at weeks 1, 9, 14, and 18 by the PI in a private area in the church. Blood pressure was taken using an Omron electronic cuff or Welch Allen manual blood pressure cuff if measures could not be obtained electronically, after participants were seated for three to five minutes. Systolic or diastolic pressures greater than 130 or 80 were considered high, 120-129 and 70-79 elevated, and less than 120 or 70 normal (American Heart Association, 2017a). Floor scales were used to measure weight. Height was self-reported for BMI calculations. BMI is a standard

measure of obesity based on an individual's weight in proportion to their height. Values greater than 29 kg/m² are considered obese, 25-29 kg/m² is overweight and 18.5-24.9 kg/m² is the normal range (American Heart Association, 2014).

Fruit and vegetable intake and physical activity were measured at weeks 1, 9, and 18 using survey items developed by the United States Department of Agriculture (USDA) Expanded Food and Nutrition Education Program (EFNEP) survey (Bradford, Serrano, Cox, & Lambur, 2010; National Institute of Food and Agriculture, 2018). Dietary intake is measured in two different ways. One is a 24 hour food recall which asks participants to write down all foods consumed in the past 24 hours, resulting in a summary of the number of vegetables and fruits eaten during that time period. The other question asks for the number of servings of fruits and of vegetables that participants think they eat each day, on average. These items are part of the entry and exit surveys normally completed by Faithful Families Thriving Communities participants and thus have been used successfully among African American churchgoers (Hardison-Moody et al., 2011). Cronbach's alpha of 0.6 at baseline, 0.7 at week nine, 0.6 at week 18, and 0.8 between all three time points showed acceptable internal consistency of the survey items used in this study. Finally, in semi structured interviews, participants were asked if any other social or environmental variables, such as access to food or places to exercise, influenced their ability to achieve their health goals.

4.5.4 Dyad Cooperation (Aim 3)

Semi-structured interviews were used to obtain an in-depth understanding of how dyads cooperated to set, pursue, and attain their goals. Prompts were guided by the two main TGDM constructs – interaction frequency, which includes, opportunities to interact,

mutual motivation, and shared goals, and goal coordination, which includes discussing challenges and coming up with strategies. Examples of prompts include ‘What were your team’s goals?’, ‘How did you and your partner motivate one another?’, and ‘Tell me about strategies you used to achieve your goals?’.

4.6 Analysis

Table 7 outlines the timeline and analysis methods for each aim.

4.6.1 Participant Characteristics

Participant characteristics obtained at baseline were analyzed using descriptive statistics (e.g., means, standard deviations). T-tests were used to identify any differences between participants who completed the program and those who did not. ANOVA and fisher’s exact statistical tests were used to identify any significant differences in baseline characteristics between participants at the different church locations.

4.6.2 Program Feasibility (Aim 1)

Feasibility survey item scores were averaged to provide a total score. The frequency of choosing ‘agree’ or ‘strongly agree’ was also calculated for each item. Dyad communication frequency was tallied from participant logs. A multilevel model (participants nested in dyads) was used to determine what, if any, characteristics (i.e., partner choice, type of partner relationship, education, age, sex, church) predicted higher feasibility scores and dyad communication frequency.

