4.4.3 Participants and Setting

The inclusion criteria for churches were faith communities with predominantly African American members in one of three counties served by Expanded Food and Nutrition Education Program (EFNEP) nutrition educators. Participant criteria were adults ages 18 years and older who identify as African American; reported being church members or regular church goers; speak, read and write English; willing to complete

study activities and assessments; and able to engage in moderate physical activity. (e.g., walking – based on their own activity level and assessment).

This feasibility study captured qualitative and quantitative data. Data from qualitative interviews generally reaches information saturation between 10-15 interviews (Guest, Bunce, & Johnson, 2006). Thus, a sample size of 20 dyads or 40 participants was planned to ensure data saturation and account for an attrition rate of 30%, as found in a meta-analysis of weight loss programs (Lemstra, Bird, Nwankwo, Rogers, & Moraros, 2016). Also, because statistical significance is not the aim of this feasibility study, a sample size of 40 was considered sufficient to allow insights into patterns of change for quantitative outcomes such as weight and physical activity (Leahey & Wing, 2012; O'Brien et al., 2015). Due to great interest, 80 members across the three sites (site one – 18 members, site two – 24 members, site three – 38 members) were enrolled.

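### The week-18 feasibility survey is summarised without accounting for paired participants who did not respond, so the acceptability figures may overstate the view of the dyad component by an unknown amount

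*Combined protocol and SAP*

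**What the plan says.** Section 4.5.2 makes participants' perception one of three feasibility domains under Aim 1 and measures it partly with a nine-item survey. On scoring it says: "The survey consists of 5-point Likert items from 1=strongly disagree to 5=strongly agree". The example items concern the partnership itself: whether the partner helped with eating habits, whether the respondent would pair with that person again, and whether the respondent helped the partner.

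Table 7 lists "Feasibility Survey Scores, Dyad communication frequency" with week 18 as the only assessment time. Section 4.6.2 gives two summaries. The first is a mean: "Feasibility survey item scores were averaged to provide a total score". The second is the agree/strongly-agree frequency, which "was also calculated for each item". A multilevel model of feasibility scores uses the same responses. The section states no denominator, response rate, rule for non-respondents or sensitivity analysis.

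Three other provisions bear on the point:

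- Section 4.4.3 plans the sample to "account for an attrition rate of 30%, as found in a meta-analysis of weight loss programs".
- Section 4.6.1 compares completers with non-completers by t-test, and Table 7 describes this as a comparison of baseline differences at week 1.
- Section 4.5.2 reports attendance and retention as a separate feasibility domain.

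**The concern.** The survey asks people to judge a partnership, and a partnership that goes badly is a plausible reason to stop taking part. If so, whether someone answers in week 18 depends on what the answer would have been, and a summary of respondents alone leans towards the satisfied.

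The other provisions do not close this gap. The completer comparison covers baseline characteristics, so it cannot show whether those who left thought less of their partner. Retention is reported, but nothing connects it to the survey percentages, so a reader will take them as the participants' opinion of the program.

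At stake is what Aim 1 can conclude about the acceptability of dyads, which are the new element under study.

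**Working it through.** **The plan's own figure.** The 30% enters only through the sample size. Section 4.4.3 expects saturation at 10–15 interviews and says "a sample size of 20 dyads or 40 participants was planned". Taking the dyad as the interview unit, 20 × (1 − 0.30) = 14 dyads, inside 10–15. In participants, 40 × 0.70 = 28, and 28 / 0.70 = 40. The planning is consistent, but it concerns interview numbers. The plan states no acceptability figure or threshold that could be reproduced.

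**Who can answer.** Under 4.4.1, partners were chosen or assigned at the end of the first nine weeks. Anyone who left before then had no partner to rate. The relevant population for the partner items is therefore everyone paired at week 10, and the relevant loss is that from pairing to week 18.

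**Inputs.**

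- d, non-response among those paired: not in the documents. Assumed 10%, 20% and 30%.
- p_R, agreement among responders: not in the documents. Assumed 70%, 80% and 90%.
- p_N, agreement among non-responders: unknown, so bounded at 0 and 1.

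**Formulas.**

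- Rate among all paired = (1 − d) × p_R + d × p_N
- Lower bound (p_N = 0) = (1 − d) × p_R
- Upper bound (p_N = 1) = (1 − d) × p_R + d
- Bias of the responder figure = p_R − rate among all paired = d × (p_R − p_N)

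**Results: bounds on the rate among all paired.**

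| d | p_R = 70% | p_R = 80% | p_R = 90% |
|---|---|---|---|
| 10% | 63% to 73% | 72% to 82% | 81% to 91% |
| 20% | 56% to 76% | 64% to 84% | 72% to 92% |
| 30% | 49% to 79% | 56% to 86% | 63% to 93% |

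For example, at p_R = 80% and d = 30%, the lower bound is 0.70 × 0.80 = 0.56 and the upper is 0.56 + 0.30 = 0.86. At d = 10%, they are 0.90 × 0.80 = 0.72 and 0.72 + 0.10 = 0.82. The width of each interval equals d, so the response rate among those paired alone tells a reader how firm the percentage is.

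**Direction.** At p_R = 80% and d = 30%:

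- non-responders at 0%: bias = 0.30 × 0.80 = +24 points
- non-responders at 50%: bias = 0.30 × 0.30 = +9 points (71% among all paired)
- non-responders at 80%: bias = 0
- non-responders at 100%: bias = 0.30 × (−0.20) = −6 points

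At d = 10% the extremes are +8 and −2 points.

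**Mean score.** The same reasoning applies on the 1–5 scale. With an assumed responder mean of 4.0 and d = 30%, the mean among all paired lies between 0.70 × 4.0 + 0.30 × 1 = 3.1 and 0.70 × 4.0 + 0.30 × 5 = 4.3.

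**The case against.** The strongest objection is that no bias has been shown. The documents give neither reasons for leaving nor the satisfaction of those who left, and the bounds allow zero or downward bias. That stands. A reader might infer that the figures are inflated because dissatisfied people dropped out, but the documents support only the possibility.

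A reader might also apply 30% loss to the 80 enrolled, get 80 × 0.70 = 56 respondents, and restate 90% agreement as 63% of everyone enrolled. That does not follow, for two reasons. The 30% is borrowed from weight loss programs as a whole and is not a forecast of survey non-response after pairing. And people who left before pairing cannot be counted as disagreeing about a partner they never had. Site one illustrates how loosely the 30% fits: 18 members enrolled make at most nine dyads, and 30% loss leaves 18 × 0.70 = 12.6 people, at most six pairs. Section 4.5.2 nevertheless reports seven dyads interviewed per church. Either loss there was smaller or dyads that had lost a member were included.

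Third, week-18 timing does not by itself restrict the survey to people attending that meeting. Follow-up of those who left is neither described nor excluded, so a responder-only summary is inferred from silence.

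Fourth, a reader might extend the criticism to the interviews. Section 4.5.2 says "Post-intervention semi-structured interviews were completed with a random sample of seven dyads" from each church and does not limit the draw to intact dyads, so that extension is unsupported.

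Finally, perception does not rest on the survey alone. Communication logs, participant interviews and educator interviews also contribute, and no threshold or go/no-go rule depends on the percentages. This lowers the stakes, but none of it supplies the missing denominator for the survey figures.

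**Conclusion.** The concern holds as a gap in the analysis of the survey. The acceptability summaries in 4.6.2 take no account of paired participants who did not respond, and nothing else in the plan lets a reader judge how much that matters. Upward bias is plausible; its presence, direction and size are not established.

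For an assumed 80% agreement among responders, the possible bias runs from 8 points too high to 2 too low at 10% non-response, and from 24 too high to 6 too low at 30%. These sizes rest on assumed values of d and of the responder rate, and on the extreme values for non-responders. If loss after pairing was small, the issue is small, and stating the two counts would show it. This is a cheap improvement; the survey itself remains usable.

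**What to change.** In 4.6.2, state the number of participants paired at week 10 and the number who answered the survey at week 18. Report each agree/strongly-agree frequency among respondents, and also among all participants paired at week 10. For the second, count non-respondents as not agreeing (lower bound) and then as agreeing (upper bound), and label it a sensitivity analysis. Do not use all enrolled as the denominator for the partner items.

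No new data collection is needed. The multilevel model already nests participants in dyads, so dyad membership should be on record, and the number of respondents comes from the returned surveys. The cost is a few added columns and a lower figure less favourable than the one among respondents.
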